Describe the characteristics of the subject population, including age range, gender, ethnic background and health status. Identify the criteria for inclusion and exclusion.

Provide the following information:

- A description of the subject selection criteria and rationale for selection in terms of the scientific objectives and proposed study design;
- A compelling rationale for proposed exclusion of any sex/gender or racial/ethnic group;
- Justification for the inclusion of vulnerable groups such as children, prisoners, adults with impaired consent capacity, or others who may be vulnerable to coercion or undue influence.

Please consider these resources:

- [NIH Diversity Policy](#)
- [FDA Diversity Guidance](#)

This study will include 70 subjects of either gender. Subjects will be randomly assigned to the following groups: (1) normal weight-bearing, massage (WB-M), (2) normal weight bearing, no massage (WB-C) (3) ULLS, no massage (U-C), and (4) ULLS, massage (U-M). Inclusion criteria are as follows: healthy subjects aged 18-30 years. Exclusion criteria include:

- BMI over 27
- Have current lower extremity musculoskeletal injuries
- Have had previous lower extremity surgeries or injury
- Activities of daily living require long periods of standing or driving a manual transmission car.
- Evidence or signs and symptoms of metabolic syndrome or disorder (diagnosis of diabetes or insulin resistance, elevated BP, high fasting blood sugar, abnormal cholesterol or triglyceride levels).
- Thyroid disorder
- Acute or chronic infections
- Use of systemic steroids, anabolic steroids, or growth hormone
- Are currently pregnant
- Have a family history of bleeding problems ("free bleeder"), as evidence by:
 - o unexplained nosebleeds (epistaxis)
 - o excessive or prolonged menstrual blood flow (menorrhagia)
 - o prolonged bleeding after minor cuts, dental procedures, tooth brushing or flossing, or trauma
- Are using medications that increase the risk of bleeding (unless it can be safely stopped):
 - o Aspirin
 - o Clopidogrel
 - o non-steroidal anti-inflammatory drugs
 - o any anticoagulation therapy (warfarin or heparin)
- Are allergic to Betadine or Xylocaine HCl.
- Any other condition or events considered exclusionary by the PI and /or physician, such as non-compliance

Attachments

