The unilateral lower limb suspension (ULLS) method has been recently developed to mimic the 0-g conditions in space and assist in assessing the efficacy of interventions to combat muscle atrophy and facilitating in-vivo muscle performance studies.¹⁰ ULLS has been shown to mimic bed rest and is a valid technique.¹¹ Just as muscle tissue responds to loading, muscle responds to unloading as well. Unloading a muscle can result in muscle atrophy at a weekly rate of about 2.5% particularly for knee extensors.¹⁰ Short term ULLS (10-16 days) doesn't seem to result in large macroscopic changes in muscle size or CSA but individual muscle fiber size has been shown to decrease at a weekly rate that varies between 3-8% across different studies.¹⁰ In specific studies, increased markers for muscle proteolysis were found after 3 days of ULLS¹⁰ and protein synthesis rate appeared to decrease after 10 days of ULLS.⁹ ULLS is a well-accepted model for disuse-induced muscle atrophy.¹⁰ There are few systemic or general deconditioning effects that have been discovered from incorporating ULLS into research procedures.¹⁰ Overall, ULLS has been shown to be a valid, practical, and cost-effective method to induce atrophy and study the effects on skeletal muscle.¹⁰

Objectives

List your research objectives. Please include a summary of intended research objectives in the box below.

The objective of this study is to determine if an optimal load of massage induces protein synthesis and increases cross sectional area

in unperturbed or atrophied human skeletal muscle tissue. In addition, we will determine whether an optimal load induces muscle damage and causes a satellite cell response in control and atrophied human skeletal muscle tissue while also examining extracellular vesicles and their possible role in a physiological phenomenon called the crossover effect. We hypothesize that 15 min of massage with a 35 N load for 4 days will not induce muscle damage but will still cause an increase of satellite cells, extracellular vesicles, as well as in cross sectional area and protein synthesis.

Study Design

Describe and explain the study design (e.g., observational, secondary analysis, single/double blind, parallel, crossover, deception, etc.).

- *Clinical Research*: Indicate whether subjects will be randomized and whether subjects will receive any placebo.

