This study is designed as a randomized control trial. Figure 1 shows the time line for the study. There will be four groups of subjects, (1) normal weight-bearing with massage (WB-M), (2) normal weight bearing without massage (WB-C) (3) ULLS, no massage (control, U-C), and (4) ULLS with massage (U-M). We expect to recruit 140 subjects to in order in fully enroll 128 (32 per group, n = 3 per group for attrition). For measurement of protein synthesis, participants will ingest three 50 mL doses of heavy water (2H2O) for the first two days and the dose will decrease to two 50 mL doses per day (a total of 1000 mL of heavy water for each subject over the course of the trial). 3-4 blood draws will be taken on days 2, 5, 7, and 9 and each will be drawn at the same time each day. Subjects in U-C and U-M groups will have their left leg immobilized and suspended using a hinged knee brace. Those immobilized will be required to wear the brace and use crutches at all times, except while showering and sleeping. Immobilization will begin on day 2 and will continue until the end of the study (day 9). Members of the research team will use a custom-made device to massage the quadriceps region of subjects' left leg and leave the right leg unaffected in the WB-M and U-M groups. Massage treatments will begin on day 3 and will take place every other day (day 5, 7, 9) until the end of the study. A baseline muscle biopsy of the vastus lateralis will be taken from the right leg on day 2, prior to the first massage. Muscle biopsies will then be taken from both legs 4-6 hours after the last massage on day 9, and the muscle tissue will be frozen for further examination. (See Figure 1). Sham treatment for the WB-C and U-C groups will include us touching the skin using a light brushing technique.

For the weight bearing groups as comparison groups, they will also have to drink deuterium oxide heavy water over 9 days which is associated with 3-4 blood draws but will not have to wear a brace or use crutches. Weight bearing control groups will only have one biopsy taken on day 9 while weight bearing massage groups will have two biopsies taken (day 2- right leg, and day 9- left massaged leg). This will still allow for effective comparison between groups and will reduce burden on these participants. We will enroll the weight bearing groups after immobilization groups to ensure that those interested in the study will not drop out after possible randomization into the immobilization group.

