Deuterium oxide heavy water ($2H_2O$) is a stable, non-radioactive isotope that is indistinguishable from normal water. It is simply water that has a higher amount of a natural, but less abundant, form of hydrogen. Subjects will be required to ingest the heavy water for 9 days. (99% D_2O , Cambridge Isotope Laboratories). A target of 1-2% enrichment is achieved during a one week priming stage and maintained for the remainder of the study. Subjects will be sent home with 50 mL doses of heavy water in sealed sterile vials. The first two days, they will consume one 50 mL vial of the heavy water three times a day (150mL/day). The next 7 days, they will consume one 50 mL vial twice a day (100mL/day). This will total 1000mL of water per subject. Over the course of the 9 day trial, the subjects' blood will be drawn on day 2, 5, 7, and 9.

Blood Draws:

Blood samples will be obtained for protein synthesis measures and for the assessment of exosomes and circulating miRNAs. Left over blood will be stored in the lab indefinitely. Approximately 5-25 ml will be drawn.

Immobilization:

Participants of the immobilization/massage and immobilization/no massage groups will be placed in a knee immobilizer on their left leg and crutches, and will be non-weight-bearing starting on day 2 (after the first two days of heavy water intake) of the 9 day trial for a total of 7 days. The participants will be required to log and explain on the attached Immobilization Time Log any time they did not use/wear the crutches or knee immobilizer in order to track compliance.

Massage:

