Participants will receive compensation based on which group they are randomly assigned to. All participants will receive \$15 for blood draws and \$50 per biopsy. Those assigned to the immobilization group will receive \$100 for unloading. The participants will receive a \$65 bonus for completion of the study for a total of \$375 if they are in the immobilization groups and \$130-\$180 for weight bearing control groups.

Costs to Subjects

Include a list of services and/or tests that will not be paid for by the sponsor and/or the study (e.g., MRI, HIV). Keep in mind that a subject will not know what is "standard" – and thus not covered by the sponsor/study – unless you tell them.

There will be no costs to the participants.

Data and Safety Monitoring

The IRB requires review and approval of data and safety monitoring plans for greater than minimal risk research or NIH-funded/FDA-regulated clinical investigations.

- If you are conducting greater than minimal risk research, or your clinical investigation is NIH-funded, describe your Data and Safety Monitoring Plan (DSMP). [Click here for additional guidance on developing a Data and Safety Monitoring Plan.](#)
- If this is a non-sponsored investigator-initiated protocol considered greater than minimal risk research, and if you are planning on using a Data and Safety Monitoring Board (DSMB) as part of your DSMP, [click here for additional guidance](#) for information to include with your IRB application.

Because this protocol involves muscle biopsy procedures, the study will be monitored by a Data and Safety Monitoring Board (DSMB). The UK CCTS has a standing DSMB and this established board will monitor this study for recruitment, adverse events, and compliance, and report to the IRB every 6 months. The DSMB is chartered to comply with the regulatory needs of a broad spectrum of

institutional protocols and are familiar with the compliance requirements of federal agencies. The DSMB will review protocol performance, regulatory requirements, particularly the reporting of adverse events, as well as documents necessary for IRB approval. The DSMB can audit protocols when necessary and communicates directly with the IRB.

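### If the weight-bearing groups are enrolled after the immobilisation groups, the ULLS effect in the two-way ANOVA is not randomised and cannot be separated from enrolment stage; massage versus sham within stage is unaffected

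*Protocol*

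**What the plan says.** **Allocation.** The protocol's subject population section says "Subjects will be randomly assigned to the following groups" and lists all four: WB-M, WB-C, U-C and U-M. The Payment section says "Participants will receive compensation based on which group they are randomly assigned to". Study Design calls the study a randomised trial, then adds "We will enroll the weight bearing groups after immobilization groups to ensure that those interested in the study will not drop out". The rest of that sentence still refers to a possible randomisation to immobilisation.

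**Biopsies (Study Design).** The general schedule is "A baseline muscle biopsy of the vastus lateralis will be taken from the right leg on day 2, prior to the first massage", followed by both legs on day 9. The weight-bearing groups are exempted from part of this: "Weight bearing control groups will only have one biopsy taken on day 9", and "weight bearing massage groups will have two biopsies taken (day 2- right leg, and day 9- left massaged leg".

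**Analysis (SAP, Statistical Design and Power).** A two-way ANOVA for ULLS and massage, with Holm-Sidak post-hoc tests, plus an unpaired t-test of U-M against U-C for the crossover effect. The SAP names no time point or leg for the ANOVA, and no stage, batch or baseline term. It sets 22 per group.

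**Objective.** "The objective of this study is to determine if an optimal load of massage induces protein synthesis and increases cross sectional area".

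**The concern.** A two-way ANOVA treats both factors alike, and in a trial described as randomised a reader will take both main effects as randomised comparisons. If the immobilisation groups are filled first, a person's ULLS status is decided by when he or she enters. Anything that differs between the two periods (who volunteers, season, staff, assay lot) is then counted as an effect of ULLS.

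The protocol gives grounds for thinking the stages could differ, though no evidence that they do. The order was chosen because of how volunteers react to possible immobilisation. Total payment is $375 in the immobilisation groups against $130-$180 in the weight-bearing groups. Participants are chosen partly on availability. COVID-19 testing applied only for part of the calendar.

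At stake is the ULLS main effect, each ULLS-versus-weight-bearing post-hoc comparison, and part of the reading of the ULLS-by-massage interaction.

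**Working it through.** **1. The SAP's sample size.** Inputs are the SAP's differences and SDs: EV number 0.29/0.294, CSA 10/11, MyoKsyn 70/76, Rab27 mRNA 150/170. Alpha and power are not stated; I assume 0.05 two-sided and 80%. A two-sample t calculation (noncentral t) gives 18, 21, 20 and 22 per group against the stated 18, 21, 19 and 22. The SAP figures are reproduced to within one, so 22 per group is used below, with the 32 per group of Study Design as a second case.

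**2. Which tissue time point is shared.** U-C and U-M have day 2 (right leg) and day 9 (both legs). WB-M has day 2 (right) and day 9 (left). WB-C has day 9 only. A four-group tissue ANOVA must therefore use day 9. This is an inference from the biopsy schedule, not an SAP statement; the SAP's sample-size table is headed % change, which WB-C tissue cannot supply.

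**3. Aliasing.** Let U = 1 for ULLS, M = 1 for massage, S = 1 for the second stage. Under sequential enrolment S = 1 − U.
- ANOVA columns 1, U, M, UM: rank 4.
- Add S: it equals the first column minus U, so rank 4 of 5.
- Add SM: it equals M − UM, so rank 4 of 6.

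No stage covariate can be estimated alongside ULLS, at any sample size.

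**4. Where a shift goes.** Suppose stage-one means differ from stage-two means by s, in SD units.
- ULLS main effect, (U-M + U-C)/2 − (WB-M + WB-C)/2: expectation is true effect + s.
- Massage within stage (U-M − U-C; WB-M − WB-C): s cancels.
- Interaction: an additive s cancels, but a massage effect that differs by stage does not.

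**5. Size, for assumed s and no true ULLS effect.** The main-effect SE is SD × √(1/n) = 0.213 SD (n = 22) or 0.177 SD (n = 32). The F test has 1 and 4(n − 1) df and noncentrality n·s².

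| s (SD) | n·s², n=22 | Rejection, n=22 | n·s², n=32 | Rejection, n=32 |
|---|---|---|---|---|
| 0.2 | 0.88 | 15.3% | 1.28 | 20.2% |
| 0.3 | 1.98 | 28.5% | 2.88 | 39.1% |
| 0.5 | 5.50 | 64.0% | 8.00 | 80.1% |

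A shift of 0.141 SD (n = 22) or 0.116 SD (n = 32) doubles the 5% error. A larger sample makes this worse.

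**6. Simulation check** (20,000 runs, n = 22, massage randomised within stage). At shifts of 0.25 and 0.5 SD the ULLS test rejects 21.5% and 64.2%, massage 4.9% and 5.1%, and the interaction 4.8% and 5.1%. With all four groups allocated concurrently, the ULLS test rejects 4.9% and 4.4%.

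**7. A stage-free ULLS contrast already collected.** In U-C on day 9, left (suspended) minus right (loaded) is within person, so s cancels. Its SE is SD × √(2(1 − ρ)/n). For assumed between-leg correlation ρ = 0.3, 0.5 and 0.7 at n = 22: √(1.4/22) = 0.252, √(1.0/22) = 0.213, √(0.6/22) = 0.165 SD. The day-9 U-C minus WB-C comparison has SE √(2/22) = 0.302 SD. Both legs have the same labelling period, so the contrast serves MyoKsyn as well as CSA.

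**The case against.** **The text does not settle the allocation.** The sentence that sets the order still mentions randomisation to immobilisation, and two other sections describe random assignment among the groups. A reader might infer that ULLS is definitely not randomised. The documents contradict themselves instead, so the finding is conditional on the stated order being followed. This objection stands.

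**The SAP names no time point.** A reader might infer that it has ruled out use of the day-2 biopsies. It is silent. For EV number, the protocol plans blood for exosomes and says "blood will be drawn on day 2, 5, 7, and 9", so a baseline may exist there. A baseline would help with a stage shift but would not make ULLS randomised.

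**The shift is hypothetical.** The population is narrow (healthy, 18-30 years, BMI not over 27), samples are coded and tissue is frozen. This stands: the table shows sensitivity and does not estimate an error rate for this trial. The aliasing itself needs no assumption about size.

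**The consequence is limited.** The objective concerns massage, and the protocol's Background presents ULLS as an accepted atrophy model. This also stands. But the SAP says it will test ULLS and follow significance with group comparisons, so the result would be reported.

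**Conclusion.** The concern holds in conditional form. If enrolment is sequential as written, the ULLS main effect and the ULLS-versus-weight-bearing comparisons are non-randomised and fully aliased with stage. The interaction is protected against an additive shift only. The inflation depends on an unknown shift: 15%, 29% and 64% rejection at 0.2, 0.3 and 0.5 SD with 22 per group.

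Two stronger readings fail. A reader might infer that the massage findings are compromised. They are not: massage versus sham within stage, including U-M against U-C, is unaffected provided massage is randomised within each stage. A reader might also infer that the effect of ULLS on protein synthesis cannot be recovered, because the day-2 sample follows only two days of labelling. That overlooks the day-9 between-leg contrast in U-C, which needs no baseline.

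That contrast has its own assumptions. It estimates ULLS under sham only. It requires that bracing the left leg leaves the right unaffected (the protocol lists soreness of the non-immobilised leg as a risk), that the legs do not differ inherently, and that the day-2 biopsy of the right leg does not alter its day-9 sample.

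**What to change.** 1. **Protocol.** Reconcile the subject population, Study Design and Payment sections. If enrolment is sequential, describe two two-arm randomisations (U-M versus U-C, then WB-M versus WB-C) and make massage versus sham within stage the randomised analysis. If all four groups are in fact allocated concurrently, say so and remove the enrolment-order sentence; the problem then disappears.
2. **SAP.** State the time point and leg for the ANOVA. Under sequential enrolment, label the ULLS main effect, all ULLS-versus-weight-bearing comparisons and the reading of the interaction as non-randomised.
3. **SAP.** Prespecify the within-person day-9 left-versus-right contrast in U-C as the stage-free ULLS estimate for CSA, MyoKsyn and any muscle mRNA, with the assumptions above stated. It does not serve outcomes measured in blood.
4. **Laboratory.** Assay stored samples from all groups in mixed batches where feasible.

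A longitudinal model using the day-2 biopsies is optional. For the sham-arm ULLS effect at n = 22 it gives SE 0.379, 0.361 and 0.341 SD at within-person correlation 0.3, 0.5 and 0.7, less precise than the between-leg contrast at the same assumed correlations, and it assumes an equal stage shift on both days.

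**Cost.** Wording, one extra analysis and some batch planning. No participants or biopsies are added and the enrolment order can stay, which matters because the continuing-review demographic table already sums to 49 enrolled. The price is that ULLS-versus-weight-bearing claims lose their randomised status.

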On day 2 of the study (after the first two days of heavy water intake), a baseline muscle biopsy will be taken from the vastus lateralis muscle of the right leg. Subjects will be instructed not to eat or drink anything for breakfast the last day of the study when they come in for the last massage and the biopsies. Subjects will be provided a light breakfast consisting of a choice of bagel with cream cheese or

granola bar or muffin with banana and orange juice. Four hours after the last bout of massage one muscle biopsy will be taken from the left and the right vastus lateralis each. Biopsies (100-300 mg tissue) will be taken by one of the two physicians on the study or the physician assistants listed in the protocol. The tissue will be frozen for analysis by the experimenters. In exercise literature a waiting period of about 2-6 hours is what is shown to demonstrate changes in the expression of genes associated with muscle size regulation.^{16,17} In an effort to respect the subjects' time, a waiting period of 4-6 hours was decided. The subjects are allowed to walk around after the massaging, but are asked to refrain from exercising for the 4 hours in between the massage treatment and the muscle biopsy.

Muscle Biopsy Procedure:

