COVID-19 testing:

During the pandemic, participants will be required to have a negative COVID-19 test before undergoing any muscle biopsy until further notice.

Attachments

Data Collection & Research Materials

In this section, please provide the following:

- Describe all sources or methods for obtaining research materials about or from living individuals (such as specimens, records, surveys, interviews, participant observation, etc.), and explain why this information is needed to conduct the study.
- For each source or method described, please list or attach all data to be collected (such as genetic information, interview scripts, survey tools, data collection forms for existing data, etc.).
- If you will conduct a record or chart review, list the beginning and end dates of the records you will view.

Demographic information

Results of blood tests after ingestion of heavy water

Analysis of muscle biopsies

Social Security Number

Attachments

Resources

Describe the availability of the resources and adequacy of the facilities that you will use to perform the research. Such resources may include:

- Staffing and personnel, in terms of availability, number, expertise, and experience;
- Computer or other technological resources, mobile or otherwise, required or created during the conduct of the research;
- Psychological, social, or medical services, including equipment needed to protect subjects, medical monitoring, ancillary care, or counseling or social support services that may be required because of research participation;
- Resources for communication with subjects, such as language translation/interpretation services.

This protocol will be performed at the CCTS. The CCTS comprises a research staff that is specially trained to make complex research observations and accurate patient assessments and documentation, to utilize precision in the collection and processing of specimens for research purposes, and to implement exemplary safe patient care practices. This unit is available to conduct research procedures for investigators throughout the institution or, under certain conditions, outside the institution.

All muscle tissue will be used in the laboratory of [name] and [name].

Potential Risks & Benefits

Risks

- Describe any potential risks – including physical, psychological, social, legal, ability to re-identify subjects, or other risks. Assess the seriousness and likelihood of each risk.

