Risk Assessment: A serious adverse event (AE) is defined as either fatal or life-threatening, requires inpatient hospitalization or prolongation of an existing hospitalization, results in persistent or significant disability/incapacity, is medically significant or requires intervention to prevent one or other of the outcomes listed above. This study is greater than minimal risk.

Grading scale for AE intensity:

Mild: Discomfort noticed but no disruption of normal daily activity.

Moderate: Discomfort sufficient to reduce or affect normal daily activity.

Severe: Incapacitating with inability to work or perform normal daily activity.

Attribution scale for AE reporting:

Probable: AE is related to the procedure (biopsies), including pain, bleeding, infection, and death, if death resulted from one of the aforementioned complications.

Possible: AE follows the biopsy within a reasonable period (within 7 days), but may have been produced by other factors.

Remote: AE does not follow the biopsy within a reasonable period (more than 7 days) and could readily have been produced by other factors.

Unrelated: AE is judged to be clearly due to extraneous causes and does not meet the above criteria.

Monitoring Plan Monitoring for adverse events will be conducted in real-time by the principal investigators and study coordinator. Risks involved with this study are considered greater than minimal risk.

AE Reporting Serious AEs will be reported verbally to the IRB and CCTS within 24 hours and in writing within 48 hours of the event. Unanticipated events will be reported to the CCTS in real time and to the IRB no later than 48 hours after the event. Annual reporting of adverse events will be conducted with the IRB annual review/renewal according to their protocol. These reports will also be forwarded to the CCTS. The CCTS Administration will be informed within 15 days if for any reason the IRB or any other body temporarily or permanently suspends the study.

Data Accuracy and Protocol Compliance All protocols involving human subjects will be directly supervised by the PI or her colleagues to assure compliance. All samples will be coded to eliminate bias. Detailed plans for maintaining subject confidentiality are described in the consent form.

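### Muscle is frozen for later assay with no stated allocation of samples to runs, and the weight-bearing groups are enrolled after the ULLS groups; assaying in order of accrual would alias run-to-run shift with the ULLS factor.

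*Protocol*

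**What the plan says.** **Tissue handling.** Protocol, Research Procedures, Muscle Biopsies: "The tissue will be frozen for analysis by the experimenters". The Study Design section says likewise that "the muscle tissue will be frozen for further examination". Neither place mentions runs, batches, plates, assay order or bridging samples.

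**Order of enrolment.** Protocol, Study Design: "We will enroll the weight bearing groups after immobilization groups". The stated reason is to limit dropout among people who might be allocated to immobilization. The subject-selection text says "Subjects will be randomly assigned to the following groups" and lists all four groups; the two statements are not reconciled.

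**Safeguard.** Protocol, Data and Safety Monitoring, paragraph on data accuracy and compliance: "All samples will be coded to eliminate bias".

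**Biopsies in the control group.** Protocol, Study Design: "Weight bearing control groups will only have one biopsy taken on day 9". WB-M has day 2 and day 9 samples; the ULLS groups have day 2 and both legs on day 9.

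**Laboratories.** Protocol, Resources: "All muscle tissue will be used in the laboratory of" two named investigators, in the singular. The Records, Privacy, and Confidentiality section uses the plural, for storage.

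**Analysis.** SAP, Statistical Design and Power: a two-way ANOVA with ULLS and massage as factors, 22 per group, and a sizing table headed as percentage change. No run or batch term appears.

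**The concern.** CSA, myofibrillar protein synthesis and Rab27 mRNA (all taken here to be measured on the biopsies) come from laboratory procedures whose readings can move between runs. Because enrolment is staged, calendar order of collection coincides with the ULLS factor. A laboratory that worked through samples as they arrived would finish the ULLS tissue before starting the weight-bearing tissue. No run would then hold both levels of ULLS, and no later analysis could separate a run shift from an effect of ULLS.

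Coding does not prevent this: a masked assayer working in order of arrival still runs ULLS tissue first.

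At stake are the ULLS main effect, which the SAP names as a target, and U-C versus WB-C, which shows whether the disuse model produced a change. A reading of U-M against WB-C as recovery to normal would also be affected. WB-C is the most exposed group, since it has no sample of its own from before day 9 against which a shift could cancel.

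**Working it through.** **1. The plan's own figure.** Inputs from the SAP table (expected difference / SD): 0.29/0.294, 10/11, 70/76, 150/170. The SAP states neither alpha nor power; I assume 0.05 two-sided and 80%. A two-sample noncentral-t calculation gives 18, 21, 20 and 22 per group against the stated 18, 21, 19 and 22. So 22 per group is reproduced and is used below.

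**2. One persistent shift aligned with ULLS.** Assumptions: raw levels in units of the within-group SD, no true ULLS effect, and a common shift s between early and late runs. The documents give no run variance, so s is assumed.

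- ULLS main effect, 44 versus 44: SE = √(2/44) = 0.2132.
- One pair such as U-C versus WB-C, 22 versus 22: SE = √(2/22) = 0.3015.
- False-positive rate = P(|Z + s/SE| > 1.96).

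| s | s/SE, main effect | Rate | s/SE, pair | Rate |
|---|---|---|---|---|
| 0.2 | 0.938 | 0.155 | 0.663 | 0.102 |
| 0.3 | 1.407 | 0.291 | 0.995 | 0.169 |
| 0.5 | 2.345 | 0.650 | 1.658 | 0.382 |

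The noncentral t gives 0.153, 0.285 and 0.640 for the main effect, and 0.099, 0.163 and 0.367 for the pair. At the 32 per group in the protocol's Study Design section the main-effect rates are 0.202, 0.391 and 0.801: more participants do not dilute an aliased shift.

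**3. Independent run effects.** Suppose instead that each run has its own effect with SD s and each stage spans six runs (assumed). Run effects add 2s²/6 to the variance of the stage difference, whose nominal variance is 2/44 = 0.0455. Rate = 2[1 − Φ(1.96·√(0.0455/(0.0455 + 2s²/6)))].

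| s | 2s²/6 | Total variance | Critical value | Rate |
|---|---|---|---|---|
| 0.2 | 0.0133 | 0.0588 | 1.723 | 0.085 |
| 0.3 | 0.0300 | 0.0755 | 1.521 | 0.128 |
| 0.5 | 0.0833 | 0.1288 | 1.164 | 0.244 |

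Run effects also inflate the residual variance, by a factor of about 1 + 5s²/6. Multiplying the critical value by the square root of that factor lowers the rates to 0.080, 0.115 and 0.201. The range is therefore about 8 to 9%, 12 to 13% and 20 to 24%.

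**4. What is not biased.** In raw levels, an additive shift common to a stage drops out of U-M minus U-C and of WB-M minus WB-C, and so out of the massage main effect and the interaction. In 20,000 simulated 2×2 ANOVAs with the shift fully aliased (0.25, 0.5 and 1.0 SD), massage and interaction tests rejected 4.8% to 5.2% of the time, while the ULLS test rejected 21.3%, 64.0% and 99.7%.

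**5. Change scores.** If each participant's samples share a run, a proportional shift multiplies both baseline and day 9 values and largely cancels in that person's percentage change. That can protect U-C, U-M and WB-M. It cannot protect WB-C.

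**6. After the fix.** With two runs balanced over all four groups and run in the model, the simulated ULLS type I error is 0.050, 0.048 and 0.049 for shifts of 0.25, 0.5 and 1.0 SD. With balanced runs but no run term it is 0.049, 0.042 and 0.028: unbiased but conservative.

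**The case against.** The strongest reply is that the harm depends on something the documents do not say. Freezing is equally consistent with collecting everything and assaying it together, and an ethics application with a one-page SAP need not set out laboratory layout. This stands in part: a reader might infer that the plan runs ULLS tissue first, and nothing in the text supports that. What remains is that nothing in the text prevents it either.

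Two further inferences should not be drawn. One is that two laboratories divide the samples and so add a laboratory shift: the Resources section has a singular noun, the plural appears only for storage, and no laboratory is tied to a level of ULLS. The other is that identification numbers follow enrolment order: this is plausible, but the protocol says only that each subject receives a number.

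On size, the 16%, 29% and 65% figures need one sustained drift acting on raw levels. Plate or stain effects that vary within a stage partly average out, as step 3 shows. The SAP table is in percentage change, and step 5 shows how far that helps. Both objections stand.

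On importance, the stated hypothesis concerns massage, and those contrasts are not biased. The protocol also expects ULLS to cause atrophy, so a false positive under no ULLS effect is not the likeliest harm; a distorted size of an expected effect is, and no figure can be put on it without a run variance. This limits the weight of the point but does not remove it, because the SAP tests the ULLS effect.

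**Conclusion.** The point holds conditionally. Staged enrolment makes collection order coincide with the ULLS factor, and neither coding nor the ANOVA keeps run shift out of that factor. If assays follow accrual, the ULLS main effect and U-C versus WB-C are biased, with WB-C most exposed.

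The size is illustrative. It assumes raw levels, 22 per group, no true ULLS effect and shifts of 0.2 to 0.5 SD: about 16% to 65% for a persistent shift, or about 8% to 24% for independent run effects over six runs per stage, against a nominal 5%.

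A reader might infer that every conclusion of the trial is threatened, or that the laboratory has made an error. The documents support neither: the assay order is unstated, and an additive shift leaves the massage effects and the interaction unbiased. It is worth correcting before the assays are run, because freezing makes the correction cheap. That no run plan exists is a statement about the supplied text only; attachments were not available.

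**What to change.** Add to the protocol's Muscle Biopsies section and its data-accuracy paragraph:

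- Frozen tissue is assayed in runs made up of whole participants, assigned at random in blocks that contain all four groups.
- Whichever samples a participant has (day 2, day 9 left, day 9 right) stay in the same run and the same laboratory for each assay.
- If some ULLS tissue has already been assayed, a leftover subset is re-run beside the weight-bearing samples as a bridge, where tissue remains.
- Storage time from biopsy to assay is recorded and reported by group.

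Add run as a block term to the SAP's two-way ANOVA. If the laboratory already mixes groups within runs, recording that and adding the term is enough.

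**Cost.** Laboratory scheduling and one model term; no new biopsies and no change in sample size. Tissue results come later, because assays wait for the second enrolment stage. ULLS tissue will also have been stored longer than weight-bearing tissue, a difference again aligned with ULLS and possibly relevant to mRNA.

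**Limit.** This removes only the assay-run component. Calendar and recruitment differences from sequential enrolment remain, and ULLS-versus-weight-bearing contrasts should be interpreted with that stated. The random-assignment and sequential-enrolment statements should be reconciled as well.
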